Aspirin as a Novel Anti-Inflammatory Modality in the Fontan Patients

NCT02966002

November 23, 2015

Background:

Over the past 40 years, one of the most important advances in the field of congenital heart disease has been the development of a long-term palliation strategy for individuals with single ventricle. Pioneers such as Fontan [1], Kreutzer[2]], de Leval [3], Bove [4], as well as many others, have contributed to creating an effective surgical palliation for individuals with single ventricle physiology by using a unique surgical reconstruction strategy of directing systemic venous blood flow to the pulmonary circulation in the absence of the pulsatile force of the sub-pulmonary ventricle. As a result of this surgical strategy, newborns with single ventricle congenital heart disease that were felt to have a near uniformly lethal type of heart disease 45 years ago, now have over a 70% chance of surviving 15-25 years after surgery. [5-8]

However, as these individuals have grown into adolescence and adulthood, it is now clear that there are significant long-term limitations with this strategy. Arrhythmias, valvular insufficiency and ventricular dysfunction are common. [9, 10] In addition there is growing evidence for a multitude of end-organ dysfunction, including poor somatic growth and development, increased risk of thromboembolism, peripheral venous insufficiency, and diabetes, protein losing enteropathy, plastic bronchitis and hepatic cirrhosis. [11-17]

Many have suggested that the combined effect of low cardiac output and increased central venous pressure are the cause of most late-complications associated with the Fontan operation. [15, 18] However, even though all Fontan patients have elevated central venous pressures and low to low normal cardiac output, these variables are not predictive of either when or which Fontan patient will develop a specific late complication.[19] For example, not all individuals with protein losing enteropathy have high central venous pressure and low cardiac outputs. [20, 21] We speculate that an alternate hypothesis for the cause of late-complications associated with the Fontan operation is that the chronic increase in central venous pressure produces generalized lymphedema, especially in the abdomen, that leads to chronic inflammation and resultant damage to many of the abdominal organs. Olszewski [22] has reported that the level of cytokines are elevated in lymphedema lymph. Olszewski also speculated that the high levels of cytokines are attributed to their local production by infiltrating immune cells. He reported that the lymph levels of cytokines, exceeded serum concentration by factors of 10 or more, and clearly point to an intensive inflammatory process in the tissues affected by the lymphedema [23]. Ostrow et al reported elevated inflammatory markers, increased TNF-alpha, CRP and C-reactive protein, in Fontan patients with protein-losing enteropathy [24]. Furthermore, Rychik reported that on endoscopic evaluation his group has found subtle evidence for inflammation/colitis in a number of individuals with protein-losing enteropathy following the Fontan operation [15]. Racz et al reported that the plastic bronchitis airway casts from children with Fontan physiology are composed of fibrin and are cellular and inflammatory in nature, providing evidence that their formation cannot be explained simply by lymph leak into the airways [25]. Consequences of cellular necrosis including extracellular histones and the apparent low number of T cells indicate that a derangement in inflammation resolution likely contributes to cast formation. There have been few reports of abnormal inflammatory markers in Fontan patients who are doing well. Zyblewski et al reported that after the Fontan operation, the plasma HDL-cholesterol levels were significantly reduced [26]. Since HDL-

cholesterol has been identified as an important anti-inflammatory mediator [27], Zyblewski et al have speculated that the low levels of HDL-cholesterol observed in their study raises the possibility that single-ventricle patients may be in a chronic inflammatory state. We have also [28] demonstrated an abnormal lipid profile in Fontan patients. We reported that Fontan patients have decreased total cholesterol, LDL-cholesterol and HDL-cholesterol, while triglycerides remain normal. In a recent study we have demonstrated that the decrease in cholesterol is related to a decrease in biosynthesis that may be mediated by inflammation (our Fontan patients had significantly higher CRP's compared to our control subjects).(unpublished data) A similar lipid profile has previously been reported in individuals with rheumatoid arthritis. Amezaga-Urruela et al [29] reported a continuous decline in total cholesterol and LDL-cholesterol has been demonstrated during the 5 years prior to the development of rheumatoid arthritis and an increase in the total cholesterol/HDL-cholesterol ratio was also observed. Increasing CRP has been negatively associated with total cholesterol and HDL-cholesterol.[30] Furthermore, in rheumatoid arthritis, as inflammations decreases with therapy, lipid levels rise. [31, 32] Based on the similar lipid profile in Fontan patients with rheumatoid arthritis patients, we hypothesis that abnormal lipids in Fontan patients are an early marker of chronic inflammation.

HDL-cholesterol levels may also relate to the pathogenesis of protein losing enteropathy. In the protein losing enteropathy patients in our study,[28]they had markedly low HDL-cholesterol and higher triglyceride levels. One determinate of HDL-cholesterol levels is lipoprotein lipase activity. [33] Blades et al [34]have reported that high hepatic triglyceride lipase and low lipoprotein lipase activity are both important contributors to low HDL-cholesterol levels in both normotriglyceride and hypertriglyceride subjects. In rheumatoid arthritis these is an inverse relation between lipoprotein lipase activity and inflammatory state. [35] Bode et al {Bode, 2005 #496} has demonstrated that loss of heparin sulfate proteoglycans from the basolateral surface of intestinal epithelial cells plays a central role in the pathogenesis of experimental meddles of protein losing enteropathy. Lipoprotein lipase is secreted by many tissues of the body, particularly metabolically active adipose tissue in the abdomen. It is transferred to the luminal surface of endothelial cells, where it is bound as homodimers to heparin sulfate proteoglycans and can be released by administration of heparin.{Lewis, 2005 #468} Therefore, if HDL-cholesterol levels are low in Fontan patients due to a decrease in lipoprotein lipases activity, based on Bode's report {Bode, 2005 #496} there may be a direct relationship between HDL-cholesterol level and protein losing enteropathy.

Abnormal lipoprotein lipase activity has also been speculated to relate to abnormal adipose tissue fatty acid trafficking and maybe part of the pathophysiological basis for ectopic fat deposition in the abdomen and heart. [36] We have recently demonstrated that Fontan patients have abnormally increased amounts of epicardial fat content when compared to age and body mass index adjusted group of patients with repaired tetralogy of Fallot. (Unpublished data)

Based on this review of the literature and our preliminary studies, we hypothesis that the abnormal lipid values in Fontan patient reflect the presence of chronic inflammation. Aspirin is a well-known agent that has been used to treat chronic inflammations associated with a number of diseases including Kawasaki's disease, rheumatoid arthritis and acute rheumatic fever. It has known to be well tolerated by both adults and children. Aspirin exerts some of its anti-inflammatory action by inhibiting the activity of I_KB

kinases- β (IKKs- β). We and others have demonstrated that aspirin can prevent or correct the insulin resistance associated with obesity.[37, 38] Pharmacologic modulation of arachidonic acid metabolites, such as aspirin, can positively modify lipid metabolism, increase HDL cholesterol. [39-41] Therefore in an attempt to test our hypothesis that the abnormal lipid values in Fontan patient reflect the presence of chronic inflammation, we plan to determine if the anti-inflammatory agent, aspirin, will normalize the lipid abnormalities in Fontan patients.

Protocol:

Patient Population: We plan to study 20 young adult subjects who have had Fontan repair of single ventricle. All subjects will be over 18 years of age and in good health. Individuals will be excluded if they have had active protein losing enteropathy within the past three years, have congestive heart failure, active arrhythmias, or on Coumadin. Any individual with a bleeding disorder or known esophageal varices will also be excluded. Subjects who known to have more than 10 drinks per week will be excluded. Females who are pregnant and /or planning become pregnant will be excluded.

Protocol: After informed consent is obtained. Subjects will have fasting blood drawn for measurement of lipids, total cholesterol, HDL-Cholesterol, LDL-cholesterol and triglycerides, a complete metabolic panel, GGT, Complete blood count and differential, plasma insulin, inflammatory markers including sedimentation rate, high sensitivity C-reactive protein and haptoglobin. Individuals will also be asked to fill out the Short-Form 36 Quality of Life Survey. Individuals will be told to stop their current 81 mg/day of aspirin, and then be started on 650 mg (two 325 mg tablets) of aspirin 2 times a day. All aspirin will be provided by use. After two weeks of aspirin therapy all individuals will have a blood salicylate level taken 6 hours after their morning aspirin dose. Goal aspirin levels will be 15-20 mg/dl. If the level is less than 10 or greater than 20 mg/dl the aspirin dose will be adjusted. All individuals will be instructed into the early symptoms of aspirin toxicity include nausea, vomiting, tinnitus, and hyperventilation. If they should experience any of these symptoms they will be instructed to immediately call us. In addition, if the individuals have any excess bleeding, blood in their stool or abdominal pain they will be told to immediately call. After 8 weeks of aspirin therapy the individual will be asked to return for repeat fasting blood test including a salicylate level and repeat the Short-Form 36 Quality of Life Survey. In addition to measuring salicylate levels, drug compliance will be monitored by pill count. All individuals will be provided with more aspirin pills than necessary for the study. They will be asked to return all the unused aspirin pills and the number of remaining pills will be counted.

Statistical analysis:

This is a pilot study to determine the safety and feasibility of a larger randomized trial. This study will form the basis for a statistically valid sample size for this planned larger trial.

Our primary outcome variable will be a change in total cholesterol and HDL-Cholesterol. It is our hypothesis that aspirin therapy will result in an increase of either total cholesterol and/or HDL-cholesterol.

Secondary outcomes: We would expect that aspirin therapy would improve the inflammatory markers (decrease high sensitivity CRP, decrease neutrophil to lymphocyte ratio, decrease sedimentation rate and decrease haptoglobin level). We also expect that aspirin will decrease plasma insulin levels and reduce the calculated HOMA-IR value [(Fasting glucose*Fasting insulin)/405; where glucose is in mg/dl and insulin is in mU/l]. We also hope that aspirin therapy might improve perception of quality of life and possibly improve liver function tests.

1. Fontan, F. and E. Baudet, *Surgical repair of tricuspid atresia*. Thorax, 1971. **26**(3): p. 240-8.
2. Kreutzer, G., et al., *An operation for the correction of tricuspid atresia*. J Thorac Cardiovasc Surg, 1973. **66**(4): p. 613-21.
3. de Leval, M.R., et al., *Total cavopulmonary connection: a logical alternative to atrio pulmonary connection for complex Fontan operations. Experimental studies and early clinical experience*. J Thorac Cardiovasc Surg, 1988. **96**(5): p. 682-95.
4. Bove, E.L. and T.R. Lloyd, *Staged reconstruction for hypoplastic left heart syndrome. Contemporary results*. Ann Surg, 1996. **224**(3): p. 387-94; discussion 394-5.
5. Earing, M.G., et al., *Long-term results of the Fontan operation for double-inlet left ventricle*. Am J Cardiol, 2005. **96**(2): p. 291-8.
6. Khairy, P., et al., *Long-term survival, modes of death, and predictors of mortality in patients with Fontan surgery*. Circulation, 2008. **117**(1): p. 85-92.
7. d'Udekem, Y., et al., *Redefining expectations of long-term survival after the Fontan procedure: twenty-five years of follow-up from the entire population of Australia and New Zealand*. Circulation, 2014. **130**(11 Suppl 1): p. S32-8.
8. Knowles, R.L., et al., *Modelling survival and mortality risk to 15 years of age for a national cohort of children with serious congenital heart defects diagnosed in infancy*. PLoS One, 2014. **9**(8): p. e106806.
9. Nakamura, Y., et al., *Ventricular performance in long-term survivors after Fontan operation*. Ann Thorac Surg, 2011. **91**(1): p. 172-80.
10. Blaurock, A.D., et al., *Functional status, heart rate, and rhythm abnormalities in 521 Fontan patients 6 to 18 years of age*. J Thorac Cardiovasc Surg, 2008. **136**(1): p. 100-7, 107 e1.
11. Cohen, M.I., et al., *Somatic growth failure after the Fontan operation*. Cardiol Young, 2000. **10**(5): p. 447-57.

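### Coumadin is the only medicine excluded, so a subject on another anticoagulant or a second antiplatelet agent meets the written criteria and can start 1300 mg/day of aspirin

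*Combined protocol and SAP*

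**What the plan says.** The Patient Population paragraph sets the sample and the entry rules:

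- "We plan to study 20 young adult subjects who have had Fontan repair of single ventricle".
- On age and general condition, the rule is: "All subjects will be over 18 years of age and in good health".
- Among those excluded are people who "have congestive heart failure, active arrhythmias, or on Coumadin".
- A further exclusion concerns bleeding: "Any individual with a bleeding disorder or known esophageal varices will also be excluded".
- The remaining exclusions are recent protein-losing enteropathy (a three-year window), alcohol above 10 drinks weekly, and current or planned pregnancy.

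The study-procedures paragraph then sets treatment and monitoring:

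- "Individuals will be told to stop their current 81 mg/day of aspirin". They then take two 325 mg tablets twice daily.
- The first scheduled level is described so: "After two weeks of aspirin therapy all individuals will have a blood salicylate level taken 6 hours after their morning aspirin dose".
- The dose rule that follows is: "If the level is less than 10 or greater than 20 mg/dl the aspirin dose will be adjusted".
- Subjects are told to call at once for unusual bleeding, blood in the stool or abdominal pain.
- "After 8 weeks of aspirin therapy the individual will be asked to return for repeat fasting blood test".

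The Statistical analysis section describes the study as a pilot for the safety and feasibility of a larger randomized trial. Inflammatory markers are secondary outcomes.

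**The concern.** The exclusion names one drug rather than the class it belongs to. The plan gives no reason for excluding Coumadin. The exclusions for bleeding disorder and varices in the same paragraph suggest, without saying so, a wish to avoid adding aspirin at this dose to an existing bleeding risk. If that is the aim, it applies equally to other anticoagulants and closely to a second antiplatelet agent, yet neither is mentioned.

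The Background gives reasons why some candidates might take such drugs: it describes a raised risk of thromboembolism after the Fontan operation and says arrhythmias are common. Only active arrhythmias are excluded. A stable subject with a past clot or a controlled arrhythmia, on an anticoagulant other than Coumadin, would pass.

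At stake is an avoidable bleeding exposure for that subject. A bleed would also be harder to interpret in a study meant to inform the safety of a larger trial.

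**Working it through.** The plan states no figure for this point, so the check is mainly a reading of the text.

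**Step 1: the dose.** From the study-procedures paragraph:

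- 2 tablets × 325 mg = 650 mg per dose
- 650 mg × 2 doses = 1300 mg/day
- 1300 / 81 = 16.0, so the starting dose is about 16 times the aspirin dose it replaces

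This dose applies to every subject. It describes the setting and does not measure the gap.

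**Step 2: each provision against the gap.**

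| Provision | Where | Does it keep out a subject on another anticoagulant or a second antiplatelet agent? |
|---|---|---|
| Coumadin exclusion | Patient Population | No. It names one drug. |
| Good health; no bleeding disorder; no known varices | Patient Population | No. These are conditions, not medicines. |
| No heart failure or active arrhythmia | Patient Population | Partly. It may remove some anticoagulated candidates, but not those treated for another reason. |
| Stopping 81 mg/day aspirin | Study procedures | No. It presumes that background but does not say it is the only antithrombotic. |
| Baseline blood count and metabolic panel | Study procedures | No. They precede dosing, but have no stated action threshold and are not a medication check. |
| Two-week salicylate level | Study procedures | No. It guides the aspirin dose, takes no account of other drugs, and follows two weeks of treatment. |
| Call-in for bleeding symptoms | Study procedures | No. It acts once symptoms appear. |

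No other part of the document gives a list of prohibited or concomitant medicines, or requires a medication review.

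**Step 3: NSAIDs, taken separately.** The parallel with Coumadin is weaker, because NSAIDs are not anticoagulants. There are two distinct issues:

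- *Added bleeding risk.* This applies to a frequent user at entry and to someone who starts during the study.
- *Secondary inflammatory markers.* The plan's own hypothesis is that an anti-inflammatory agent improves them, so an NSAID begun between baseline and week 8 is a competing cause of change. A stable user takes the drug at both measurements, so the change is not confounded in that way. An entry exclusion does not deal with new use; an instruction during the study does.

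**The case against.** The strongest reply is that few people, perhaps none, would pass through this gap. Subjects are young adults in good health without heart failure, active arrhythmias, a bleeding disorder or known varices, and the procedures treat low-dose aspirin as the usual background. Coumadin may simply be the one alternative the authors foresaw. Consent pages are not in the public file, and medication advice might appear there. All of this stands as an argument about frequency. None of it alters what the eligibility rule permits.

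A second reply is that, with no control arm, a bleed in any subject would be hard to attribute, and that recording co-medication would be a smaller remedy than exclusion. The first half is fair: a second drug adds to a limitation already present. Recording would help describe a case but would not prevent the exposure.

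Stronger readings are tempting and are not supported:

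- *That the risk can be sized* from the aspirin taken before the two-week check, or from how far one bleed among 20 would move a crude proportion. Both would be the same for a fully eligible subject on no other drug, and the plan defines no bleeding proportion.
- *That the plan intends to enrol such subjects.* The text is silent; it does not invite them.
- *That NSAID use is an equal problem.* It is secondary, for the reasons in the check.
- *That the primary result is compromised.* Nothing in the documents links this gap to the lipid outcome.

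**Conclusion.** The point holds as a defect in a stated entry rule. As written, a subject on an anticoagulant other than Coumadin, or on an antiplatelet agent besides aspirin, is eligible for 1300 mg/day, and every later safeguard acts after treatment has begun. Because safety is a stated purpose of the pilot and one line closes the gap, the change is worth making.

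Its size is unknown. The documents give no frequency of co-medication, the described population makes it probably low, and no bleeding risk can be calculated. The conclusion rests on the eligibility and procedures text alone. It assumes that Coumadin was excluded because of bleeding risk, which the neighbouring exclusions suggest but do not state. The sample size and the analysis of total and HDL cholesterol are not in question here.

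**What to change.** 1. In the Patient Population paragraph, replace the Coumadin wording with: *on any anticoagulant, or any antiplatelet agent other than the 81 mg/day aspirin being replaced*.
2. Check each candidate's medication list at entry, before the first study dose.
3. As a secondary step, exclude NSAID use on a defined basis, for example daily or near-daily use at entry. An undefined term such as regular use would leave the criterion ambiguous.
4. Add to the existing call-in instructions that subjects should not start an anticoagulant, antiplatelet agent or NSAID during the 8 weeks without calling the study team. This limits added bleeding risk and a competing cause of change in the inflammatory markers.

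The cost is a short eligibility edit, one entry check and one added sentence of instruction. A few candidates may be excluded and need replacing to fill the 20 places. The study dose stays as planned, and no one is asked to stop an existing treatment beyond the aspirin the plan already replaces. The change reduces the exposure but cannot remove it, since a subject may still start such a drug without calling.

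### The exclusions do not name a past gastrointestinal ulcer or bleed, although the study starts aspirin at 1300 mg/day in place of 81 mg/day

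*Combined protocol and SAP*

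**What the plan says.** All entry criteria are in the Patient Population paragraph. The general health requirement is "All subjects will be over 18 years of age and in good health", and good health is not defined further. The bleeding-related exclusions are Coumadin use and the sentence "Any individual with a bleeding disorder or known esophageal varices will also be excluded". The remaining exclusions cover protein losing enteropathy active in the last three years, heart failure, current arrhythmia, drinking above ten drinks a week, and pregnancy (present or planned).

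The Protocol paragraph sets the treatment. Subjects "stop their current 81 mg/day of aspirin, and then be started on 650 mg (two 325 mg tablets) of aspirin 2 times a day". The dose check is described as "After two weeks of aspirin therapy all individuals will have a blood salicylate level taken 6 hours after their morning aspirin dose", with the rule "If the level is less than 10 or greater than 20 mg/dl the aspirin dose will be adjusted". On bleeding, the instruction is "if the individuals have any excess bleeding, blood in their stool or abdominal pain they will be told to immediately call".

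The Statistical analysis section gives the purpose: "This is a pilot study to determine the safety and feasibility of a larger randomized trial".

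**The concern.** The plan treats bleeding as a hazard in two places. It bars some people at entry because of bleeding risk, and during treatment it tells subjects to report signs that point to the gut. The entry list covers clotting problems, one specific lesion and one anticoagulant. It leaves out the most direct history for the hazard that the warning addresses, namely a previous ulcer or bleed in the gastrointestinal tract.

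What is at stake is the safety of any such subject, who could be moved to a much higher aspirin dose while every written criterion is followed. A question at consent would have identified the history. Because the pilot is meant to inform the safety of a larger trial, its entry criteria may also be carried forward.

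**Working it through.** **Step 1. The dose.** The inputs come from the Protocol paragraph: two tablets of 325 mg, taken twice a day, replacing 81 mg/day.

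- Per intake: 2 × 325 mg = 650 mg, which matches the plan's stated figure.
- Per day: 650 mg × 2 = 1300 mg. The plan does not print this daily total.
- Ratio to the previous dose: 1300 / 81 = 16.05.

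This is the starting dose. It may change after the two-week salicylate level.

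**Step 2. Would a subject with a past ulcer or gut bleed be stopped at entry?** Take an adult Fontan patient with a healed ulcer or a resolved gut bleed and no other relevant condition, and compare this person with each criterion that might apply.

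| Criterion | Does it exclude this subject? |
|---|---|
| Over 18 and in good health | Not clearly. It is undefined, and a resolved problem is compatible with good health. |
| Bleeding disorder | No, on the ordinary meaning of a clotting or platelet disorder. |
| Known esophageal varices | No. This is one specific lesion. |
| Coumadin | No, unless the subject happens to take it. |
| More than ten drinks a week | No, unless it happens to apply. |
| Protein losing enteropathy, heart failure, arrhythmia, pregnancy | No. These are unrelated to the history in question. |

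The subject is eligible as written.

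**Step 3. Does current aspirin use act as a screen?** The Protocol paragraph speaks of subjects stopping their current 81 mg/day, which implies that they already take it. This is not listed among the entry criteria. Even if every subject takes it, it shows only that someone considered low-dose aspirin acceptable. It does not record whether there was a past ulcer or bleed, and it was not a judgement about 1300 mg/day.

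**Step 4. Does anything else before dosing pick up the history?** The baseline visit draws blood, including a blood count, and collects a quality-of-life questionnaire. Neither asks about a past ulcer or bleed, and no entry threshold is attached to the blood results. The two-week salicylate rule acts on drug level and comes after dosing has begun.

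**Step 5. Can the effect be sized?** Sizing it needs the proportion of eligible subjects with this history and their bleeding rate at each dose. The documents give neither, so no expected number of events is calculated.

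**The case against.** The strongest reply is that the group left exposed is small. The plan already acts before exposure by excluding bleeding disorders, known varices, Coumadin users and heavier drinkers. Subjects appear to be on daily aspirin already, so people judged unfit for any aspirin are largely filtered out. The good-health requirement also gives the investigator room to decline someone with a worrying history. What remains is young adults with a past ulcer or bleed who are still on daily aspirin and judged healthy. No passage of the plan says how much that history adds to risk.

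Most of this stands. It limits the weight of the point and rules out any claim about expected harm. It does not close the gap, because none of these filters asks about the history, and the investigator's discretion is unwritten.

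A reader might go further in four ways that the documents do not support:

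- **Reading the 16-fold ratio, or the total grams taken over eight weeks, as a measure of risk.** These figures describe the regimen and would be the same after the clause is added.
- **Quoting the wide confidence interval around one event in 20 subjects as the size of the problem.** That interval applies to any single event in any group of 20, whatever the entry criteria.
- **Treating the lack of a stated blood test between the two-week salicylate level and week 8 as part of this point.** That is a question about monitoring, and an eligibility clause would not change it.
- **Extending the point to cirrhosis or portal hypertension without documented varices.** Whether to bar those subjects is a clinical choice that would narrow the population and could leave less room to see improvement in liver tests, which the plan hopes for. The documents do not point to a definite change.

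**Conclusion.** The point holds as a narrow eligibility gap. As written, a subject with a past gastrointestinal ulcer or bleed can meet every criterion and start 1300 mg/day in place of 81 mg/day. The plan's own call-at-once instruction shows that it regards gut bleeding as a hazard of this treatment.

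The conclusion rests on two assumptions. The first is that a bleeding disorder means a clotting or platelet disorder and does not stretch to a past ulcer or bleed. The second is the general clinical view that such a history matters when aspirin is raised to this level, which is reasonable but not sourced in the documents.

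The size is unknown. It could be no subjects among the 20 or a few, and the documents cannot say which. No design number, endpoint or analysis changes. A reader might infer that the pilot is unsafe or has no protection against bleeding, but the documents do not support that: several pre-dosing exclusions and a call-at-once instruction are in place. The clause is worth adding because it is cheap and concerns subject safety, not because a harm has been demonstrated.

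**What to change.** Extend the bleeding sentence in the Patient Population paragraph so that, besides bleeding disorder and known varices, it excludes a history of peptic or other gastrointestinal ulcer or of clinically significant gastrointestinal bleeding. Check this from the chart and by asking the subject at consent. The qualifier of clinical significance keeps a trivial remote bleed from barring entry. If the clinical team prefers a look-back period, the plan already uses one of three years for protein losing enteropathy.

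The cost is one clause and a history question, with no new procedure or visit. Somewhat more people may need to be screened to enrol 20, probably only slightly more, although the documents give no figure to confirm that. The results would not apply to people with this history, and undiagnosed disease would still be missed.

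### The only scheduled aspirin dose decision, at week 2, rests on salicylate alone; adding a blood count to that draw is a cheap safety improvement

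*Combined protocol and SAP*

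**What the plan says.** All of this is in the combined protocol and SAP.

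- **Baseline (Protocol section).** The fasting draw includes "a complete metabolic panel, GGT, Complete blood count and differential". Subjects then stop 81 mg/day and start 650 mg twice daily.
- **Week 2 (Protocol section).** "After two weeks of aspirin therapy all individuals will have a blood salicylate level taken 6 hours after their morning aspirin dose". No other week-2 test is listed. The goal is 15-20 mg/dl, and the rule is: "If the level is less than 10 or greater than 20 mg/dl the aspirin dose will be adjusted". The rule carries no hemoglobin or blood-count condition.
- **Week 8 (Protocol section).** "After 8 weeks of aspirin therapy the individual will be asked to return for repeat fasting blood test including a salicylate level". The blood count is not named again, but a repeat of the baseline panel would contain it. The secondary outcomes also need a follow-up differential, since one of them is "decrease neutrophil to lymphocyte ratio".
- **Between visits (Protocol section).** Subjects are taught the early symptoms of aspirin toxicity and asked to report them. For bleeding, "if the individuals have any excess bleeding, blood in their stool or abdominal pain they will be told to immediately call".
- **Entry (Patient Population).** Subjects must be in good health, and Coumadin users and heavier drinkers (above 10 drinks weekly) are left out. On bleeding risk, the section adds: "Any individual with a bleeding disorder or known esophageal varices will also be excluded".
- **Purpose (Statistical analysis).** The study is presented as a pilot on the safety and feasibility of a larger randomized trial.

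**The concern.** The protocol treats bleeding as a risk of the study dose, since it tells subjects which bleeding symptoms to report. That safeguard works only for bleeding the subject notices. Slow loss that goes unnoticed would show as a fall in hemoglobin, and no hemoglobin value is scheduled while it could still change study dosing.

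Week 2 is where this matters most. It is the only scheduled point at which the dose may change, and the change depends on one number. A subject below 10 mg/dl would presumably be given more aspirin, and a hidden fall in hemoglobin would not enter that decision. At stake are the safety of individual subjects and, to a lesser degree, the pilot's safety data, which would hold no early on-treatment hemoglobin value.

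**Working it through.** The plan gives no figure to reproduce here. The check is a reading of the schedule, followed by simple arithmetic.

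**Dose (Protocol section).** 2 x 650 = 1300 mg/day, against 81 mg/day before: 1300/81 is about 16 times higher.

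**Schedule (Protocol section).**

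| Time | Salicylate | Blood count | Dose decision |
|---|---|---|---|
| Baseline | not listed | yes | start 1300 mg/day |
| Week 2 | yes | not listed | adjust if <10 or >20 mg/dl |
| Week 8 | yes | inferred | none described |

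Scheduled counts after baseline and before week 8: 0. Time on a dose changed at week 2 before the next scheduled test: 8 - 2 = 6 weeks, or 6/8 = 75% of treatment.

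**Inferences.** (a) The text says only that the dose is adjusted; with a goal of 15-20 mg/dl, an adjustment below 10 sensibly means an increase. (b) The week-8 draw includes a count, from its description as a repeat and from the neutrophil-to-lymphocyte outcome. Without one the gap would be larger. (c) Dosing ends at week 8, from the stated 8 weeks of therapy and the return of unused pills; no later dosing is described.

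**How much a week-2 count could gain.** Assume that onset of blood loss is uniform over 0-8 weeks and that a fall becomes measurable L weeks after onset. Neither assumption comes from the documents.

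- Share of onsets measurable at week 2 = (2 - L)/8
- Gain for each of these = 8 - 2 = 6 weeks
- Mean gain over all onsets = 6 x (2 - L)/8

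| Lag L (weeks) | Share caught at week 2 | Mean gain over all onsets (weeks) |
|---|---|---|
| 0 (upper limit) | 2/8 = 25% | 1.5 |
| 1 | 1/8 = 12.5% | 0.75 |
| 2 | 0/8 = 0% | 0 |

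These are shares of any bleeding that occurs. They cannot be turned into a number of subjects, because no bleeding rate is given.

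**False alarms.** Assume that ordinary within-subject hemoglobin change is normal with no true fall, and that the threshold is a multiple of its SD. Expected chance flags among 20 subjects:

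- at 2 SD: 20 x P(Z > 2) = 20 x 0.02275 = 0.46
- at 3 SD: 20 x P(Z > 3) = 20 x 0.00135 = 0.03

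The documents do not give that SD, so these figures do not say how large a fall, in g/dl, either threshold would detect.

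**The case against.** The best case for the plan is that this is a reasonable monitoring choice for 20 healthy adults over 8 weeks. Entry criteria remove the most obvious bleeding risks. Subjects appear to be taking low-dose aspirin already. The 20 mg/dl ceiling at week 2 is itself a scheduled check on exposure. Subjects are told when to call, and nothing prevents an unscheduled count. The Background also describes aspirin as well tolerated. No interval promised by the plan is missed, and no planned analysis fails.

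Most of this stands, and it limits the point to a suggestion. It does not remove the gap. An unscheduled count needs a trigger, and unnoticed loss supplies none. The exclusion covers only known varices, while the Background lists hepatic cirrhosis among Fontan complications. The tolerability remark is general and not specific to 1300 mg/day in this population. A salicylate level measures exposure, not blood loss.

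A second objection is that the remedy is partial. That also stands: a week-2 count sees at most the first quarter of treatment, and nothing that follows a dose increase. The gain could be nil.

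A reader might infer that the plan is in error, or that bleeding would go undetected for 8 weeks. The documents support neither reading. Noticed bleeding has a reporting route, extra tests are not barred, and nothing in the documents shows that such bleeding is likely.

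**Conclusion.** The point holds as an optional, low-cost improvement. On the text, the week-2 dose decision uses salicylate alone, and no count is scheduled between baseline and week 8. A dose could therefore be raised in a subject with unnoticed blood loss, with the next count arriving too late to alter study dosing. This rests on the three inferences listed in the working.

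The size is modest: 0% to 25% of onsets caught earlier, with a mean gain over all onsets of 0 to 1.5 weeks, under assumed uniform onset and a 0-2 week lag. It would be tempting to conclude that a week-2 count closes the monitoring gap. It does not, because losses that begin later stay unseen until week 8. Its main value is that the one scheduled dose decision would be made with a current hemoglobin in hand.

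**What to change.** Add a complete blood count to the existing week-2 draw for all 20 subjects, with these rules:

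1. Raise no dose until the count has been reviewed.
2. For a level above 20 mg/dl, reduce at once without waiting for the count.
3. Before enrolment, fix the hemoglobin fall from baseline that triggers holding or reducing study aspirin and evaluating the subject, whatever the salicylate level. If study aspirin is held, the investigator decides whether and when to return to 81 mg/day, because the Background lists thromboembolism among Fontan complications.
4. If salicylate is rechecked after an increase, draw a count at the same time. The plan schedules no such recheck before week 8.

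State the limit beside the rule: the week-2 count detects only falls already measurable by then, and without step 4 later losses, including those after an increase, remain unseen until week 8.

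The cost is 20 assays at a draw every subject already has, with no new visit, plus one assay for each recheck under step 4. Increases would wait briefly. Occasional false alarms would bring a work-up and interrupted dosing, which is a real cost in a 20-subject pilot; the threshold should be chosen with that in mind.
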